2.0 Background and Significance

2.1 Background

Transition from hospital to home places complex patients in jeopardy of adverse events and increases their risk for use of urgent care (emergency department visits and hospitalizations). In a study of Medicare patients, nearly 20% were rehospitalized within 30 days¹, and similar results have been found at VHA facilities². Patients and their families are unprepared for what awaits them at home³, partially due to deficiencies in transferring information and supporting self-management⁴⁻⁷.

For Veterans with CHF or COPD, the transition from hospital to home is a vulnerable period, placing them at great risk for adverse event and risk of rehospitalization. Nurse inperson care transition interventions are effective, but are resource intensive. Few CTIs have used advanced patient-directed technologies, an effective means to augment care transition interventions. The relational agent and tailored communication technologies that we will evaluate are a means to overcome the constraints of traditional nurse-based/home visit centric interventions and will make it feasible to coach Veterans with CHF or COPD on an ongoing basis, regardless of their distance from VA facilities.

Patient-level care transitions can be supported through multi-component, evidence-based interventions⁸⁻¹². Parker and colleagues performed a systematic review to study characteristics associated with improved care transitions¹³ and decreased urgent care use. Many of these interventions focused individually or on a combination of discharge planning, discharge support, geriatric assessment, and educational approaches.

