recruitment, we propose to extract data, our primary effectiveness measure (urgent care utilization) and dates. This is a pre-post difference in differences analysis, comparing the number of urgent care utilizations per month before and after the index-hospitalization where randomization occurred. For this analysis, the outcome for each individual is a count of urgent care utilizations. We will use a count regression with the dependent variable being the post-hospitalization count of urgent care, using the pre-hospitalization count as a covariate in the model. For this outcome, we will also construct a linear regression model using the mean change in the number of urgent care utilizations by randomization group. Finally, we will conduct an interrupted time series analysis using the times of the urgent care utilization, the randomization treatment group, a marker for pre versus post-index hospitalization. In this model, we will look for a significant difference in change in the slope of urgent care utilizations pre-post-index hospitalization by randomization group. We will evaluate sustained community tenure, (number of days out of 30 days that the Veteran is in their own home (as opposed to inpatient or in the emergency department). For this measure, we will first explore the distribution of the outcome to assess whether it fits best as a count distribution or a difference in mean proportion of days. We will then conduct a bivariate analysis with the dependent variable (sustained community tenure) and the independent variable (randomized group assignment).

Power Calculations:

For our primary outcome measure, we first estimated a mean number of urgent care visits (ED and hospitalization) for the six months pre-randomization and six months postrandomization for each patient. We know that readmission rates are between 12.7% and 21% annually for our Veterans, and ED visits will be similar or higher per year (thus urgent care use = 25%-40%). Thus, we estimate a monthly rate of urgent care use of 3% (40% annual/12 months) of our sample of 600 patients (thus a mean of 18 utilizations per month). Using a pre-intervention rate of 18 for both intervention and control, and a postcontrol change of 1, assuming an alpha of 0.05, and we have power (0.8) to detect a difference of differences in change in mean urgent care utilization of 0.75 with a standard deviation equal to the control mean.

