For Aim 2, our goal is to recruit 600 Veterans from among 1,913 with COPD/CHF as primary diagnosis and then expand to those within the total pool of 19,128 who have secondary diagnoses of CHF/COPD at the four study sites (Boston, Hines, Iowa City, Palo Alto). Participants will be recruited at each study site (Boston, Iowa City, Hines, Palo Alto). Using the national sample of Veterans actively receiving VHA services available in the Corporate Data Warehouse, nationally, in 2013, there were over 435,700 Veterans with a diagnosis of CHF, and over 73,000 of them had at least one admission to a VHA facility (as primary diagnosis or secondary). Similarly, in 2013, there were over 789,500 Veterans with a diagnosis of COPD, and over 151,300 of them had an admission to a VHA facility. Thirty-day readmission rates for Veterans with CHF and COPD vary, but are in general higher than national averages. Based on statistics from the VHA Support Service Center (Inpatient Evaluation Center (IPEC)) Reports, there were a total of 1,147 Admissions for CHF, and 765 for COPD in 2013 (approximately 10% of all admissions). We will prioritize recruitment of patients with a primary admission diagnosis of CHF/COPD. If recruitment is falling below goal, we will also include patients with a secondary diagnosis of CHF/COPD admitted on general medical services. Thus, our goal is to recruit 600 Veterans from among 1,913 with COPD/CHF as primary diagnosis and then expand to those within the total pool of 19,128 who have secondary diagnoses of CHF/COPD at the four study sites.

Post-Clinical Trial Data Analysis:

For our formative evaluation (Aim 3), we will conduct semi-structured interviews with clinical staff at our study sites. Interviews will be organized and scheduled by the discharge assistants. We will work with the discharge assistants and site PIs in advance of each visit to compile a list of inpatient clinical staff and other key informants (e.g., quality improvement officers). The discharge assistants will identify appropriate participants. Recruitment of other clinical staff and key informants will proceed through an accumulative or “snowball” sampling strategy in the course of the interviews. Recruitment will continue until 1) there is redundancy in referrals and 2) we have sufficient data to support our implementation goals. We plan to recruit 12-15 participants from each site. All interviews will be conducted under the approval of the Bedford IRB, using Bedford

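### The annual readmission rate behind the primary power is not reconciled with the protocol's 30-day statements, and the stated 80% power does not follow from the plan's own inputs

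*Combined protocol and SAP*

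**What the plan says.** Section 3.5 (Power Calculations) bases the primary power on the mean number of urgent care visits, ED and hospital together, in the six months on either side of randomization. The chain is:

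- Readmission: "We know that readmission rates are between 12.7% and 21% annually for our Veterans".
- ED use is taken as at least equal to this, so urgent care use becomes 25% to 40% a year.
- The monthly figure: "we estimate a monthly rate of urgent care use of 3% (40% annual/12 months) of our sample of 600 patients", hence "thus a mean of 18 utilizations per month".
- The power inputs: "Using a pre-intervention rate of 18 for both intervention and control, and a postcontrol change of 1", with an SD equal to the control mean and alpha 0.05. The result is power of 0.8 for a between-arm difference in change of 0.75.

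Elsewhere the protocol describes the timing of readmission differently:

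- Section 2.1, on a study of Medicare patients: "nearly 20% were rehospitalized within 30 days". It adds that VHA facilities show similar results.
- Section 4.5: "Thirty-day readmission rates for Veterans with CHF and COPD vary, but are in general higher than national averages".
- Section 4.1, repeated in Section 4.6.2.2: readmission is frequent in these patients, above all in the first month at home.

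The planned primary model in Section 3.5 is a count regression of each patient's later events, adjusted for the earlier count. Follow-up after discharge is six to twelve months.

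**The concern.** Cumulative risk over twelve months cannot be lower than risk over the first 30 days in the same kind of patients. The power paragraph gives an annual range whose lower end lies below the protocol's own 30-day figure and whose upper end barely exceeds it. The annual label is the only reason for dividing by 12, and the quotient becomes both the base rate of 18 and the SD.

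Urgent care utilization is the primary effectiveness measure, and this paragraph states the power of its between-arm comparison. If the base rate has no clear period and the power does not follow from it, a reader of a null result cannot tell what size of reduction the trial could have detected.

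**Working it through.** **Inputs.** From Section 3.5: readmission 12.7% to 21%, equal ED use, 600 patients, base rate 18, difference 0.75, SD equal to the control mean, alpha 0.05, power 0.80. The primary paragraph gives neither the number per arm nor the sidedness. I take 300 per arm and a two-sided test, as the same section does for community tenure. From Section 2.1: nearly 20% at 30 days.

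**1. The plan's base rate.** 40%/12 = 3.33% per month, or 20 in 600. The plan rounds to 3%, and 0.03 × 600 = 18. The lower figure of 25% gives 25/12 = 2.1%, so 3% lies inside the plan's own range. This is rounding and nothing rests on it.

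**2. The plan's power.** Power = Φ(δ / (SD × √(2/n)) − 1.96).

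- With SD 18 and n = 300: SE = 18 × √(2/300) = 1.470; 0.75/1.470 = 0.510; Φ(0.510 − 1.96) = **0.074**. One-sided it is 0.128.
- SD 17 to 19 (18 moved by the control change of 1): 0.078 to 0.070.
- SD 9 (18 split over two arms): 0.174.
- SD √18 = 4.24 (Poisson-type): 0.581.
- SD 1 (if the control mean is the control change of 1): about 1.00. Power of 0.80 then needs only 28 units per arm.

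At SD 18 the difference detectable with 80% power is 2.80 × 1.470 = 4.12, and 9,042 per arm would be needed to detect 0.75. Power of 0.80 with 300 per arm requires SD 3.28, which is not an input in the plan. None of these readings reproduces the stated figure.

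The units do not fit either. The 18 is a monthly total for all 600 patients, yet it is applied to each arm in a paragraph that speaks of a mean per patient.

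**3. Annual against 30-day.**

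- Read as annual and flat: 12.7%/12 = 1.06% and 21%/12 = 1.75% per month, or about 6 to 11 of 600 readmitted each month.
- Section 2.1 figure applied to this sample: 20% × 600 = 120 in the first month.
- With 20% readmitted by day 30, a yearly 12.7% is impossible. A yearly 21% leaves 21 − 20 = 1 point, or 6 of 600 patients, for day 31 to day 365.

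**4. Size if the range is a 30-day figure (assumption), with equal ED use.**

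- First month: 2 × 12.7% = 25.4% and 2 × 21% = 42%, or 152 to 252 events in 600 patients.
- Six-month average with no event at all after day 30: 152.4/6 = 25.4 and 252/6 = 42 per month.
- Against 18: 25.4/18 = 1.4 and 42/18 = 2.3. This is a floor.

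**5. What 300 per arm can detect in a count model.** Solve |ln RR| = 2.80 × √(1/(300μ) + 1/(300μ·RR)), where μ is the control mean per patient over six months (Poisson, no overdispersion, no covariate).

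| μ | Source | Detectable RR |
|---|---|---|
| 0.18 | 3% × 6 | 0.521 |
| 0.20 | 40%/2 | 0.544 |
| 0.254 | floor, 12.7% at 30 days | 0.591 |
| 0.42 | floor, 21% at 30 days | 0.675 |

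Overdispersion adds 2k/300 under the root. At μ = 0.20, assumed k of 1 and 2 give 0.52 and 0.49.

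**6. Direction.** In the count model a higher rate moves the detectable ratio closer to 1. Under the plan's rule that the SD equals the mean, it does the opposite: the detectable absolute difference goes from 4.12 at 18 to 5.8 at 25.4 and 9.6 at 42.

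**The case against.** The documents do not prove the base rate wrong. The figure of nearly 20% comes from Medicare patients, the VHA comparison carries no number, Section 4.5 gives none, and the source of 12.7% to 21% is not cited. The plan's 3% also comes from the upper end, and 21% in a year is implausible beside 20% in a month but not impossible. All of this stands. It limits the point to an unreconciled input.

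Three stronger readings are tempting, and the documents do not support them.

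- A reader might infer that 12.7% to 21% simply is a 30-day range. That is plausible, but no section says so.
- A reader might set a first-month rate of 25% to 42% against 3% and call the base rate 8 to 14 times too low. That compares a one-month peak with an average, whereas the power window is six months. The supportable ratio is the floor of 1.4 to 2.3; anything larger needs later rates that the documents do not give. Readmission after discharge also says nothing direct about use before the index stay, so the pre-period 18 is not contradicted.
- A reader might infer that the mislabelled rate leaves the trial underpowered. In the count model the plan intends to fit, a higher rate helps.

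It is also fair to say that the detectable ratios above omit the pre-hospitalization covariate and any follow-up beyond six months. They are illustrations, not replacements for the plan's figure.

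**Conclusion.** Two separate faults stand in the primary power paragraph.

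First, the annual label on 12.7% to 21% is not reconciled with Sections 2.1, 4.1 and 4.5, so 3% per month (18 per month) is unsupported for the post-discharge period. Its size depends on an assumption: if the range is a 30-day figure and ED use equals it, the six-month average is at least 25 to 42 per month, 1.4 to 2.3 times the 18.

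Second, and without that assumption, the stated power of 0.80 does not follow from the plan's inputs. With SD 18 and 300 per arm it is about 0.07 to 0.08. Correcting the period alone would not repair it.

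No single corrected power can be given, because later rates and overdispersion are not in the documents. The finding is that the stated power cannot be relied on. It does not show that the trial is too small.

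**What to change.** 1. State the source and time window of 12.7% to 21%, and reconcile it with Sections 2.1, 4.1 (with 4.6.2.2) and 4.5.
2. Replace the calculation with a per-patient one based on the planned count regression over the actual six to twelve months of follow-up. Use separate rates for the first month and later months. Label the later rates and the overdispersion as assumptions, and show a range for each.
3. State the number per arm and the sidedness, and restate the detectable rate ratio for 300 per arm. The Poisson values at 0.20, 0.254 and 0.42 events per patient in six months can serve as a check. Note that a higher rate improves the ratio.

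The cost is one rewritten paragraph and a short recalculation. Enrolment, data collection and the primary model do not change.

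### The power statement for the primary outcome mixes whole-sample monthly totals with per-patient counts, leaves the unit of 0.75 and the SD undefined, and cannot be reproduced as written

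*Combined protocol and SAP*

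**What the plan says.** Section 3.5 (Analysis Plan) states that "the outcome for each individual is a count of urgent care utilizations". The planned model is a count regression of the post-hospitalization count, "using the pre-hospitalization count as a covariate in the model".

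The Power Calculations text in the same section proceeds as follows:

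- It says it estimated a mean number of urgent care visits "for the six months pre-randomization and six months postrandomization for each patient".
- It gives an annual urgent care use of 25% to 40% and turns the upper end into 3% per month "of our sample of 600 patients (thus a mean of 18 utilizations per month").
- It continues: "Using a pre-intervention rate of 18 for both intervention and control", adds a control change of 1 and an alpha of 0.05, and claims power of 0.8 "to detect a difference of differences in change in mean urgent care utilization of 0.75 with a standard deviation equal to the control mean".

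The paragraph does not give the number per arm, sidedness, pre-post correlation, formula or test. A later paragraph, on 30-day community tenure, uses 300 per group and a two-sided 0.05. Between the two, a claim based on 24 to 36 months of data gives an effect size of 0.5 with autocorrelation between 0.0 and 0.2.

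**The concern.** The text starts per patient, moves to a monthly total for the whole sample, and then treats that total as the mean in each arm. The difference of 0.75 could be visits per patient, events per month in an arm or in the sample, percentage points, or SD units. The SD could be 18, 17 or 19 (18 with the control change of 1 in either direction), 9, or 1 (the control change itself).

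This is the sample-size justification for the primary outcome. If the unit and the SD are unknown, a reader cannot tell what effect the trial was planned to detect, and a null result cannot be judged against it.

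Two inputs are also unclear:

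- **Windows.** The power text uses six months each side. The analysis text in Section 3.5 has 18 months before and 6 to 12 after. The time-series paragraph goes back up to 24 months.
- **Readmission rate.** The plan says "We know that readmission rates are between 12.7% and 21% annually for our Veterans". Section 2.1 cites nearly 20% within 30 days for Medicare patients and says VHA results are similar. Section 4.5 says 30-day rates for these Veterans are generally above national averages, without a percentage. Whether 12.7% to 21% is an annual or a 30-day figure needs confirming.

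**Working it through.** **Scale of the inputs**

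- Whole sample: 0.03 × 600 = 18 per month, as printed. Without rounding, 40%/12 = 3.33%, and 3.33% × 600 = 20.
- One arm of 300: 0.03 × 300 = 9 per month, not 18.
- One patient: 0.03 per month, or 0.03 × 6 = 0.18 over six months. A reduction of 0.75 is 0.75/0.18 = 4.2 times this mean, so it is impossible on the per-patient six-month scale.

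**Attempt to reproduce the stated power**

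Two-sample t-test, difference 0.75, n = 300 per arm (600/2), two-sided 0.05, noncentrality = 0.75 / (SD × √(2/300)):

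| SD | Possible meaning | Power for 0.75 |
|---|---|---|
| 18 | pre-intervention rate as stated | 8.0% |
| 17 or 19 | control rate after a change of 1 | 8.4% or 7.7% |
| 9 | monthly total in one arm | 17.5% |
| √18 = 4.24 | Poisson SD of 18 | 58.0% |
| 1 | control change | above 99.9% |

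Power of 80% needs an SD of 3.27, which the text does not give. With SD 18, the difference detectable at 80% power is 4.12.

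**Readings that come near 80%**

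- *Percentage points per month.* SD 3.33 gives 78.6% and SD 3 gives 86.4%. However, the Poisson SD of a patient's six-month average monthly rate r is √(6r)/6. That is 7.07 points at r = 0.03 and 7.45 at r = 0.0333, and power is then 25.4% or 23.4%.
- *Monthly totals as units.* SD 1 with 29 units per arm gives 80.1%. The paragraph states no such number of units.

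**What the planned count regression could detect (illustration)**

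The detectable rate ratio (RR) at 80% power solves

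−ln(RR) = 2.80 × √[(1/μ + k_r)/300 + (1/(μ·RR) + k_r)/300],

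where μ = monthly rate × months of follow-up and k_r = k/(1 + k·μ_pre). Here μ_pre is the mean pre-index count over 18 months. The overdispersion k = 0, 1, 2 is assumed, and all of it is taken as stable variation between patients.

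| Control rate | μ_pre | 6 months | 12 months |
|---|---|---|---|
| 3% per month | 0.54 | 0.521, 0.505, 0.497 | 0.651, 0.623, 0.612 |
| 25%/12 = 2.08% | 0.375 | 0.436 to 0.415 | 0.588 to 0.551 |
| 40%/12 = 3.33% | 0.60 | 0.544 to 0.519 | 0.667 to 0.627 |

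A simulation at 3% per month (2,000 runs; Poisson model with log pre-count covariate and robust standard errors) gave power of 0.81 to 0.82 at about these ratios.

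If the true rate were much higher, say an assumed 20% per month over 6 months, the detectable ratio would be 0.80 (Poisson). With k = 1 to 2 it would be 0.73 to 0.75 if the mean pre-count is 0.54, and 0.78 if it is 3.6.

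**Power of that model for 0.75 under each reading**

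- Against 18: 0.75/18 = 4.2%, RR 0.958. Power is 5.5% to 6.1% at 3% per month with 6 to 12 months of follow-up.
- Against 9: 0.75/9 = 8.3%, RR 0.917. Power is 6.9% to 9.6%.
- Against 3.33 percentage points: 0.75/3.33 = 22.5%, RR 0.775. Power is about 21% to 45% at 3% to 3.33% per month.

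**The case against.** The best defence is that the figure can nearly be recovered. The plan prints the division of 40% by 12, which is 3.33%. An SD equal to that mean, in percentage points, gives 78.6% power for 0.75. In a difference of differences with equal baselines, the baseline and the control change cancel, so ignoring the 18 and the 1 is not in itself a fault. Monthly totals are a second route: the time-series paragraph has 24 to 36 months of data, a range that includes 29, and with SD 1 power runs from 72% to 88% across it.

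Both near-matches are real, and they are why the finding is that the statement cannot be interpreted rather than that 80% is impossible. Neither rescues it. The percentage-point reading needs a unit the sentence does not state and an SD about half the Poisson value for a per-patient rate. The monthly reading needs an unstated number of units and a particular choice of SD, and the monthly series carries its own effect size of 0.5, with no unit or power level. Neither corresponds to the per-patient count regression.

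It can also be said that this is version 16, dated February 2021, with the trial period given as ending in summer 2020, so the calculation can no longer guide recruitment. That is fair, and it is why an annotation would do. The stated figure still frames how the result will be read. The illustrative ratios do rest on a 3% rate that is itself in question and on an assumed overdispersion.

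**Conclusion.** The concern holds. The power claim for the primary outcome mixes scales, does not define the unit of 0.75 or the SD, and does not follow from its inputs. At 300 per arm and two-sided 0.05, the SD values considered give anything from about 8% to above 99.9%. This does not establish the trial's true power.

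At the plan's own 3% per month, the planned model would detect reductions of roughly 35% to 50%, depending on follow-up of 12 or 6 months and on overdispersion from none to k = 2. None of the three readings of 0.75 set against a baseline (18, 9 or 3.33 points) gives that model 80% power at 3% to 3.33% per month. A higher true control rate would make smaller reductions detectable.

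**What to change.** Replace the 0.75 claim, or annotate it if the planning record should be kept, with a per-patient detectable rate ratio for the count regression adjusted for the pre-index count. State:

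- 300 per arm, two-sided 0.05 and 80% power.
- One follow-up window and one pre-period, reconciled across the analysis and power text of Section 3.5.
- The overdispersion assumption, for example from pooled blinded pre-index counts.
- The control rate, saying whether 12.7% to 21% is annual or 30-day, and correcting the rounding (40%/12 × 600 is 20, not 18).

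Label the effect size of 0.5 as a separate time-series claim and give its unit and power.

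The cost is rewording and a short recalculation. The sample size stays at 600, and the design and planned analyses do not change. The downside is that the stated detectable effect will probably look less favourable.

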Our recruitment will occur over 24 months, post-discharge number of months of data will vary between six and twelve, and will extend back in time for up to 24 months, resulting in a total number of months between 24 and 36 for urgent care utilization. With these assumptions, we are powered to detect an effect size of 0.5 with an autocorrelation between 0.0 and 0.2.

Assuming a baseline rate of 1.0 and the mean exposure time to be 30 days, a sample of 300 patients in each group will achieve 80% power at a two-sided alpha level of 0.05 to detect a rate ratio of at least 1.0425. This calculation is based on a Poisson Regression with the number of 30-day sustained community tenure counts as the dependent variable and randomized group as a binary independent variable.

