We will work with the discharge assistants and site PIs in advance of each visit to compile a list of inpatient clinical team members and other key informants (e.g., quality improvement officers). Recruitment of other clinical staff and key informants will proceed through an accumulative or “snowball” sampling strategy in the course of the interviews. Recruitment will continue until 1) there is redundancy in referrals and 2) we have sufficient data to support our implementation goals. We plan to recruit 12-15 participants from each site. All interviews will be one-on-one, semi-structured, and audio-recorded, lasting about 30 minutes. In conjunction with the start of each interview, participants will be asked to complete a short questionnaire to document their professional background, training, and work experience. Interview topic areas addressed will include current care transition practices, programs, and related interventions at the facility, use of technology to support care processes, characteristics of the clinical environment and corresponding implications for implementing novel, technology-based interventions, and pros and cons of using the kinds of technology specific to the Annie intervention to interact with older patients. All Aim 3 data will be analyzed at both ENRM VA and Hines VAMC.

The patients we are recruiting are in-hospital CHF and COPD patients. For sick patients with these conditions, rehospitalization is a common occurrence, especially within 30 days of leaving the hospital. The intervention that we have designed and are testing in this study is intended to help Veterans with CHF and COPD take better care of themselves post-discharge, and to reduce hospital readmissions. For these reasons, in this study, we consider rehospitalization a serious but anticipated adverse event that will be reported at each annual IRB continuing review and DSMB report as required.

We will not note hospital readmissions in patient charts as an adverse event since participants are being re-admitted by their physician. If the admission is unrelated to the research procedures, a research progress note about their readmission would not be useful for subject’s clinical care.

Serious and unanticipated adverse events such as data breach or death will continue to be reported to IRB immediately.

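### The power statement for 30-day community tenure sets the reference arm at the 30-day maximum, so the effect it claims to detect (31.3 days out of 30) cannot occur

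*Combined protocol and SAP*

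**What the plan says.** Section 3.5 (Analysis Plan) defines sustained community tenure as the "number of days out of 30 days that the Veteran is in their own home", "as opposed to inpatient or in the emergency department". The outcome therefore runs from 0 to 30. For the analysis, the plan will first look at the distribution and "assess whether it fits best as a count distribution or a difference in mean proportion of days".

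The Power Calculations part of the same section gives one power statement for this outcome. It begins "Assuming a baseline rate of 1.0 and the mean exposure time to be 30 days", takes 300 patients per group, and concludes that this sample "will achieve 80% power at a two-sided alpha level of 0.05 to detect a rate ratio of at least 1.0425". The method is given as follows: "This calculation is based on a Poisson Regression with the number of 30-day sustained community tenure counts as the dependent variable", with randomized group as a binary predictor. The unit of the baseline rate is not stated, and no mean, SD or overdispersion value for tenure appears anywhere in the documents.

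Two other sections bear on the baseline. Section 2.1 reports that among Medicare patients "nearly 20% were rehospitalized within 30 days", with similar results at VHA facilities. Section 4.1 says of the trial's own population that "rehospitalization is a common occurrence, especially within 30 days of leaving the hospital".

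**The concern.** A rate of 1.0 over 30 days, for an outcome counted in days at home, reads as every reference patient being at home on every day. That is the ceiling, and a ratio above 1 has nowhere to go. A Poisson model also sets the variance equal to the mean, whereas an outcome that cannot exceed 30 must have less and less variance as its mean approaches 30.

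What is at stake is how the tenure result is read. If tenure shows no difference, a reader would turn to this statement to see what size of effect the trial could have found. A figure that describes an impossible effect cannot serve that purpose. In addition, if the count option were run as an ordinary Poisson model with model-based standard errors, the variance mismatch would carry over into the test itself.

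**Working it through.** **Inputs, all from section 3.5.** Baseline rate 1.0; exposure T = 30; 300 per group (N = 600, equal allocation); power 80%; two-sided alpha 0.05; stated ratio 1.0425; outcome range 0 to 30 days.

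**1. Reproduce the plan's figure.** The usual sample-size formula for Poisson regression with a balanced binary covariate, with b = ln(ratio), is

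N = (1.960 x √4 + 0.842 x √(2 + 2e^(−b)))² / (T x rate x b²).

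At a ratio of 1.0425, b = 0.04162 and √(2 + 2e^(−b)) = 1.980. The numerator is 5.586² = 31.20 and the denominator is 30 x 0.04162² = 0.05197, so N = 600.4. Solving for the ratio at N = 600:

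| Reading of the baseline rate | Expected count | Detectable ratio |
|---|---|---|
| 1.0 per day | 30 | 1.0425 (matches the plan) |
| 1.0 per 30 days | 1 | 1.2526 (does not match) |

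Other common two-sided versions of the calculation give 1.0422 to 1.0426 at an expected count of 30 and 1.24 to 1.26 at an expected count of 1. The arithmetic is right for its inputs, and those inputs put the reference mean at 30 of 30 days.

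**2. Compare with the cap.** 30 x 1.0425 = 31.3 days, above the maximum of 30. Conversely, 30 / 1.0425 = 28.8 days is the highest reference mean at which the ratio is attainable, and there it requires every patient in the other arm to be at home for all 30 days. The largest attainable ratio is 30/m:

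| Reference mean m (days) | 30 | 29.5 | 29 | 28.5 | 28 |
|---|---|---|---|---|---|
| Largest possible ratio | 1.000 | 1.017 | 1.034 | 1.053 | 1.071 |

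**3. Check the variance.** An outcome between 0 and 30 with mean m has variance at most m(30 − m). The Poisson model assumes variance m.

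| Mean m (days) | Largest possible variance | Poisson variance |
|---|---|---|
| 30 | 0 | 30 |
| 29.5 | 14.75 | 29.5 |
| 29 | 29 | 29 |
| 28.5 | 42.75 | 28.5 |
| 28 | 56 | 28 |

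Above a mean of 29 the Poisson variance is necessarily too large. Below 29 the true variance may lie on either side. At a mean of 28, for example, the SD can be anything up to 7.48 days, against a Poisson SD of 5.29.

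**4. Can the direction be settled?** Not from the documents. An illustrative simulation allowed at most one readmission per patient, on a uniformly distributed day, with a geometric length of stay cut off at day 30, no home days after death and no ED days. Every input is assumed:

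| Readmitted / mean stay / mortality | Mean (days) | SD (days) | Poisson SD ÷ actual SD |
|---|---|---|---|
| 20% / 6 days / 0% | 29.0 | 2.77 | 1.94 |
| 20% / 6 days / 5% | 28.3 | 4.63 | 1.15 |
| 20% / 6 days / 8% | 27.8 | 5.42 | 0.97 |
| 30% / 10 days / 5% | 27.2 | 5.75 | 0.91 |

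Above 1, a model-based Poisson test is conservative; below 1, it is anti-conservative.

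**5. What 300 per group would detect in days.** Detectable difference = 2.80 x SD x √(2/300). Assumed SDs of 2, 4 and 6 days give 0.46, 0.91 and 1.37 days, a threefold spread that depends wholly on an SD the plan does not give.

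**The case against.** The strongest reply is that the Poisson formula hardly depends on the baseline. At reference means of 28.5, 28 and 27 days the same equation gives ratios of 1.0436, 1.0440 and 1.0449, that is 29.7, 29.2 and 28.2 days in the other arm. All are attainable, and the detectable difference stays near 1.2 days against 1.28 in the plan. This is true: for means of about 28.7 or lower, correcting the baseline alone makes the statement possible. It does not make the statement informative, because it still takes the variance to equal the mean, and the detectable difference is driven by the SD.

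The conflict with the rehospitalization figures can also be pressed too far. With 20% readmitted, an assumed 6-day stay and no deaths, the mean is still 29.0 days, so common readmission is compatible with a mean near 30. But 29.0 is not 30, and at 29.0 a ratio of 1.0425 would still need 30.2 days.

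The plan's check of the distribution answers part of the analysis worry. Nothing commits the trial to model-based Poisson errors, so that harm is conditional. The check governs the later choice of model, however. It does not repair the power statement, and the mean-proportion option has no power statement at all.

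It is fair to add that the simulated stays and mortality appear nowhere in the documents and that the change of direction rests on them. The bound m(30 − m) makes the point without the simulation. It is also fair that after recruitment a confidence interval tells the reader more than a power figure.

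**Conclusion.** The concern holds. The stated ratio of 1.0425 rests on a reference mean of 30 of 30 days and implies 31.3 days in the other arm, which is impossible. It can occur only if the reference mean is at most 28.8 days. The Poisson variance cannot hold at a mean of 30 and is too large at any mean above 29; at lower means the direction of the error is unknown.

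Reading the rate as 1.0 per day is an inference, since the unit is not stated, but of the two readings only this one reproduces the plan's figure. The fault lies in the inputs, not the arithmetic.

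The scope is limited. Tenure is not primary (section 3.5 names urgent care utilization), and the primary power statement and the target of 600 do not depend on this calculation. Section 3.3 places the trial period between Spring 2017 and Summer 2020, and this version is dated February 24, 2021, so a restated figure would serve the reading of the result rather than recruitment. It should be fixed on that footing.

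**What to change.** Withdraw the 1.0425 statement. In its place, give the detectable difference in mean days (or mean proportion of days) at home for 300 per group, from an explicit control mean below 30 and an explicit SD with its source, shown over a range. The target difference must fit between the control mean and 30. The 0.46 to 1.37 days above (SD 2 to 6) shows the form of such a statement; it is not a proposed value.

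For the analysis, name the difference in mean days or mean proportion, which section 3.5 already lists, with robust or bootstrap standard errors and a confidence interval in days. Do not rely on model-based Poisson standard errors. State how days after death are counted, since the illustration shows that this can change the SD materially.

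The cost is SAP wording and one recalculation. The one piece of extra work is finding a source for the SD, because the documents contain none; the SD of tenure with both arms pooled, from data the plan already collects, would serve. No new data collection and no change to enrolment is needed.
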